5.3.1. Definition

The primary efficacy endpoint is the change in MADRS total score from Day 1 (prerandomization) to end of the 4-week double-blind treatment phase (Day 28).

The MADRS is a clinician-administered scale designed to measure depression severity and detects changes due to antidepressant intervention. (Montgomery 1979) The scale consists of 10 items, each of which is scored from 0 (item not present or normal) to 6 (severe or continuous presence of the symptoms). Higher scores represent a more severe condition. The MADRS evaluates reported sadness, apparent sadness, inner tension, reduced sleep, reduced appetite, concentration difficulties, lassitude, inability to feel, pessimistic thoughts, and suicidal thoughts. The test exhibits high inter-rater reliability. The typical recall period for the MADRS is 7 days.

The MADRS total score is the sum of scores from individual question items at a given time point, and ranges from 0 to 60. Higher scores represent a more severe condition. Imputation of total score is presented in section 5.1.4.

Negative changes in MADRS total score indicate improvement.

One estimand is defined for the primary endpoint: Primary Estimand.

5.3.2. Primary Estimand

Primary Trial Objective: To evaluate the efficacy of each individual dose of esketamine nasal spray, 56 mg and 84 mg, compared with placebo nasal spray in improving depressive symptoms in participants with TRD who have met nonresponse criteria, as assessed by the change from baseline in the Montgomery-Asberg Depression Rating Scale (MADRS) total score from Day 1 (prerandomization) to end of the 4-week double-blind treatment phase (Day 28).

Estimand Scientific Question of Interest: What is the antidepressant benefit from each individual dose (56 mg and 84 mg) of esketamine nasal spray compared with placebo nasal spray in improving depressive symptoms in participants with TRD who have met nonresponse criteria based on the change in the Montgomery-Asberg Depression Rating Scale (MADRS) total score from Day 1 (prerandomization) to end of the 4-week double-blind treatment phase (Day 28) if the participants take study intervention as directed?

The primary estimand is defined by the following 5 components:

Study Intervention:

• Experimental: esketamine 56 mg, esketamine 84 mg

• Control: Placebo

Population: Participants with TRD who have met the inclusion/exclusion criteria and the nonresponse criteria

Variable: Change from baseline to Day 28 in the MADRS total score

Summary Measure: Difference in means between each dose and placebo for the change from baseline in MADRS total score at Day 28.

Intercurrent events and their corresponding strategies:

Intercurrent Events	Name of Strategy for Addressing Intercurrent Events and Its Description
Premature discontinuation of the randomized treatment with or without a switch to alternative antidepressant	Hypothetical strategy: as if the intercurrent event had not occurred
treatment	

5.3.2.1. Analysis Methods

5.3.2.1.1. Primary Analysis

Descriptive statistics of the actual values and the change from baseline to each postbaseline time point in the double-blind phase will be presented for MADRS total score by intervention group.

MADRS total score will be analyzed by a Mixed-Effect Model for Repeated Measures (MMRM) based on observed case data. The fixed terms included in the model will be intervention group, analysis center, antidepressant treatment status (on- or off-treatment) at screening entry, day, and day-by-intervention interaction, and the baseline MADRS total score as a covariate. The within-subject covariance between visits will be estimated via an unstructured variance-covariance matrix. In case of convergence problems, alternative variance-covariance structures will be tried in the following order, with the first structure that converges being used in the analysis: heterogeneous Toeplitz, standard Toeplitz, and AR(1) with separate subject random effect. In the case that a structured covariance needs to be used, a robust sandwich variance estimator of heterogeneous Toeplitz, standard Toeplitz, and AR(1) will be used to address the potential adverse impact of covariance matrix mis-specification on the estimation and testing of treatment effect. Comparison between each dose of esketamine nasal spray and placebo nasal spray at Day 28 will be performed using the appropriate contrast. Difference in least square means and 2-sided 95% CI will be presented for each dose level.

Means and mean changes from baseline (+/- SE), and least squares mean changes from baseline (+/- SE) over time will be presented graphically.

Model Diagnostics

The normality and equal variance assumptions underlying the primary MMRM model will be assessed graphically for the MADRS total score at Day 28. Residuals from the primary models will be plotted against the predicted values and a QQ plot of the residuals versus the expected quantiles of the standard normal distribution will be presented. If either the equal variance or the normality assumption appears to be grossly violated, other methods including an ANCOVA on ranks model or an appropriate transformation of the primary endpoint might be considered.

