1.3. Schedule of Activities (SoA)

Screening and Double-blind Phases

Phase	Screening							Double-blind									
	Week	1	2	Optional weeks for tapering/DC ^a		2-week antidepressant-free period ^b		1		2		3		4			
Day						Day -14 to -8	Day -7 to -1	1	2	4	8	11	15	18	22	25	28/EW
Visit Window (days)		±2		±2		±2	±2		+2	±1	±1	±1	±1	±1	±1	±1	±1
Visit	1.1	1.2 ^c	1.3	1.4	1.5	1.6 ^c	1.7	2.1	2.2	2.3	2.4	2.5	2.6	2.7	2.8	2.9	2.10
Clinic visit (C) or Telephone contact (TC)	C	C	C/TC ^a	C/TC ^a	C/TC ^a	C	C	C	C	C	C	C	C	C	C	C	C
Study Procedure																	
Screening/Administrative																	
Informed consent (ICF)	X																
ICF for optional pharmacogenomic research samples	X																
Demographics	X																
Medical and psychiatric history	X																
Employment Status	X																
Inclusion/exclusion criteria ^d	X							X									
MINI	X																
IDS-C ₃₀	X																
MGH-ATRQ	X																
SAFER Interview		X															
Prestudy therapy	X																
Preplanned surgery/procedure(s)	X																
Height	X																
Study Intervention Administration																	
Randomization								X ^d									
Practice session for use of nasal spray device								X ^e									
Dispense/administer study intervention								X		X	X	X	X	X	X	X	
Study intervention accountability								X		X	X	X	X	X	X	X	

Phase	Screening								Double-blind									
	Week	1	2	Optional weeks for tapering/DC ^a			2-week antidepressant-free period ^b		1		2		3		4			
Day							Day -14 to -8	Day -7 to -1	1	2	4	8	11	15	18	22	25	28/EW
Visit Window (days)		±2					±2	±2		+2	±1	±1	±1	±1	±1	±1	±1	±1
Visit	1.1	1.2 ^c	1.3	1.4	1.5		1.6 ^c	1.7	2.1	2.2	2.3	2.4	2.5	2.6	2.7	2.8	2.9	2.10
Clinic visit (C) or Telephone contact (TC)	C	C	C/TC ^a	C/TC ^a	C/TC ^a		C	C	C	C	C	C	C	C	C	C	C	C
Study Procedure																		
Efficacy Assessments																		
MADRS (7-day recall), video teleconferencing	X	X ^{f,g}					X ^g	X ^{g,h}	X ^{g,h}			X ^g		X ^g		X ^g		X ^g
MADRS (24-hour recall), video teleconferencing												X ⁱ						
CGI-S	X								X ^e	X		X ^e		X ^e		X ^e		X
PHQ-9 (patient-reported)							X		X ^e				X ^e					X
Safety Assessments																		
Physical examination	X								X ^e									X
Vital signs predose if applicable (blood pressure, heart rate, temperature)	X						X	X ^h	X	X	X	X	X	X	X	X	X	X
Vital signs postdose (blood pressure, heart rate) ^j									X		X	X	X	X	X	X	X	
Weight	X																	X
12-lead ECG	X								X ^e									

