- d. Minimum criteria for the availability of documentation supporting the eligibility criteria are described in Source Documentation in Appendix 3, Regulatory, Ethical, and Study Oversight Considerations. Verify inclusion/exclusion criteria before randomization of each participant.
- e. Predose (if applicable) and at the actual dosing day. On Day 1 performed pre-randomization.
- f. Must be completed prior to start of tapering or discontinuation of current antidepressant treatment.
- g. The MADRS should be administered no more than 2 days prior to the subject's targeted (not actual) clinic visit date (except Visit 2.1, which is within 1 day prior). If performed on the day of the scheduled clinic visit with an intranasal treatment session, the MADRS must be performed prior to the intranasal treatment session.
- h. If Visit 1.7 and Visit 2.1 are performed on the same day, Visit 1.7 procedure can be omitted (ie, will be performed only as part of Visit 2.1).
- i. The Day 2 MADRS assessment must be administered within the Day 2 to Day 4 window and prior to Day 4 intranasal treatment session.
- j. Performed at $t = 40$ minutes and $t = 1.5$ hours postdose, $t = 0$ is the time of the first spray of nasal spray study medication.
- k. Collected at $t = 40$ minutes and $t = 2$ hours postdose, where $t = 0$ is the time of the first spray of nasal spray study medication.
- l. The pharmacogenomic samples (DNA and RNA) should be collected at the specified time point predose under fasting condition, however, if necessary the sample may be collected at a later visit (predose, fasting) without constituting a protocol deviation.

For Participants Receiving Esketamine: Open-label Treatment/Observation Phase and Follow-up Phase

Phase	Open-label Treatment/Observation Phase														Follow-up		
Week	5		6		7		8		9	10	11	12	13	14	15	16	~ 1 week after last visit
Day	28	31	35	38	42	45	49	52	56	63	70	77	84	91	98	105	-
Visit window	±2	±2	±2	±2	±2	±2	±2	±2	±3	±3	±3	±3	±3	±3	±3	±3	
Visit	3.1	3.2	3.3	3.4	3.5	3.6	3.7	3.8	3.9	3.10	3.11	3.12	3.13	3.14	3.15	3.16	4.1
Clinic visit (C)	C	C	C	C	C	C	C	C	C	C	C	C	C ^a	C	C ^a	C	C
Study Intervention Administration																	
Recommended dosing frequency	Twice weekly ^b								Weekly ^b				Weekly or every other week ^b				
Dispense/administer study intervention	X	X	X	X	X	X	X	X	X	X	X	X	X	X	X	X	
Study intervention accountability	X	X	X	X	X	X	X	X	X	X	X	X	X	X	X	X	
Efficacy Assessments																	

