9.4.2. Primary Endpoint

Primary Estimand

The primary estimand, the main clinical quantity of interest to be estimated in this study, is defined by the following 5 components:

- **Population:** participants with TRD who have met the inclusion/exclusion criteria and the nonresponse criteria
- **Endpoint:** change from baseline to Day 28 in the MADRS total score
- **Treatment:** placebo, esketamine 56 mg, esketamine 84 mg
- **Intercurrent Events:** All intercurrent events leading to changes in randomized treatment, such as premature discontinuation of the randomized treatment with or without a switch to

alternative antidepressant therapies, will be handled by a hypothetical strategy to estimate what the outcome would have been if all participants adhered to their randomized treatment. That is, post-treatment observations will not be included in the primary analysis.

- **Population Level Summary:** the difference in means between each dose and placebo for the change from baseline in MADRS total score at Day 28.

Missing data will be closely monitored and if necessary, to assess the robustness of conclusions from the primary analysis to missing data assumptions, additional sensitivity analyses and/or estimands will be specified in the SAP. The key assumption in the primary analysis is that missing data arise from a Missing at Random (MAR) mechanism. This assumption is aligned with the estimand and the hypothetical strategy.

The primary efficacy variable, change from baseline in MADRS total score at Day 28, will be analyzed using a Mixed-Effect Model for Repeated Measures (MMRM) model based on observed case data. The model will include factors for treatment (esketamine 56 mg, esketamine 84 mg, placebo), center, antidepressant treatment status (on- or off-treatment) at screening entry, day, day-by-treatment interaction, and baseline MADRS total score as a covariate. The within-participant covariance between visits will be estimated via an unstructured variance-covariance matrix. Comparisons of the esketamine groups versus placebo will be performed using the appropriate contrast.

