5.3.2.1.2. Sensitivity Analysis

To evaluate the robustness of the MMRM analysis to increasing deviations from the MAR assumption, a delta adjustment multiple imputation method will be implemented on the MADRS total score if the results from the primary analysis show a significantly greater improvement in

MADRS total score at Day 28 in each dose of esketamine nasal spray compared to placebo. (National Research Council 2010; Permutt 2015)

This method will employ the following 3 steps:

Step 1 – Multiple Imputation (MI)

Missing at random (MAR) is assumed for intermediate missing data (ie, missing data between non-missing observations). If there are participants with a non-monotone missing data pattern, datasets with only monotone missing data patterns will be created first by imputing the intermediate missing values using methods such as the MCMC (Markov Chain Monte Carlo) method. Five hundred (500) imputations will be performed to create 500 unique datasets which now have monotone missing (ie., missing data after the participant experienced an intercurrent event) data pattern. This will be done using SAS PROC MI and the MCMC statement with the following specifications (in case of non-convergence, analysis center will be removed from the following model):

```
PROC MI DATA=INPUT NIMPUTE=500 SEED=234 OUT=IN MCMC;
```

VAR ...; (intervention group, analysis center, antidepressant treatment status, and the preceding non-missing values in the order of clinical visits: baseline, Day 2, Day 8, Day 15, Day 22 and Day 28)

MCMC CHAIN=SINGLE NBITER=200 NITER=100 IMPUTE=MONOTONE; RUN;

Monotone missing data will first be imputed by MAR-based MI regression, and the imputed scores in the experimental intervention groups will be adjusted to be worse than the other participants in same group with non-missing data as discussed below. The multiple imputation will be performed using SAS PROC MI with the MONOTONE statement and the REGRESSION option with the following specifications (in case of non-convergence, analysis center will be removed from the following model):

```
PROC MI DATA=IN_MCMC NIMPUTE=1 (see note) SEED=234 OUT=OUTPUT; BY IMPUTATION;
```

VAR ...; (intervention group, analysis center, antidepressant treatment status, and the preceding non-missing values in the order of clinical visits: baseline, Day 2, Day 8, Day 15, Day 22 and Day 28)

CLASS ...; (intervention group, analysis center, antidepressant treatment status) MONOTONE REGRESSION;

RUN:

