5.4.1.3. Analysis Methods

The key secondary efficacy variable, change from baseline in MADRS total score at Day 2 in the double-blind treatment phase, will be analyzed using the same MMRM model as described for the primary endpoint.

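### The primary MMRM assumes one baseline MADRS slope for Days 2 to 28; letting it vary by visit costs four parameters and may add a little precision

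*SAP*

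**What the plan says.** The fixed terms in SAP 5.3.2.1.1 are intervention, analysis center, antidepressant status at entry, "day, and day-by-intervention interaction, and the baseline MADRS total score as a covariate". Protocol 9.4.2 has the same structure: "day, day-by-treatment interaction, and baseline MADRS total score as a covariate". In both, day interacts with treatment only, and no other section adds a baseline-by-day term. The covariance is free by visit: "The within-subject covariance between visits will be estimated via an unstructured variance-covariance matrix".

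The key secondary Day 2 contrast comes from this model too; SAP 5.4.1.3 says it "will be analyzed using the same MMRM model as described for the primary endpoint".

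The Schedule of Activities (Protocol 1.3) has two MADRS rows. One is "MADRS (7-day recall), video teleconferencing", used at baseline and Days 8, 15, 22 and 28. The other is "MADRS (24-hour recall), video teleconferencing", marked once with footnote i. The table columns did not extract cleanly, but the footnote ties that row to Day 2: "The Day 2 MADRS assessment must be administered within the Day 2 to Day 4 window", before the Day 4 session. Day 2 therefore follows a single dose. SAP 5.3.1 mentions only the typical 7-day recall.

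The imputation in SAP 5.3.2.1.2 regresses each visit on "the preceding non-missing values in the order of clinical visits: baseline, Day 2, Day 8, Day 15, Day 22 and Day 28". It therefore estimates a separate baseline coefficient at each visit.

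**The concern.** A main-effect baseline term says that a one-point difference at baseline predicts the same difference in outcome one day after the first dose and four weeks later. The two visits differ in time since baseline, number of doses and, at Day 2, recall period, so equal slopes are an untested assumption.

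If the slopes differ, the common slope is a compromise. Some Day 28 variance that baseline could explain stays in the residual, and likewise at Day 2. What is at stake is a little precision on the two controlled contrasts.

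**Working it through.** **1. The plan's own figures.** Protocol 9.2 gives a difference of 5.4, SD 12, 142 placebo and 71 per dose.

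- SE = 12 × √(1/71 + 1/142) = 1.744, and 5.4/1.744 = 3.10.
- Two-sided power is 87.2% at 0.05 and 80.4% at 0.025.
- The Hochberg rule on two z-statistics with correlation 1/3 (shared placebo arm; 2 million draws) gives 85.8% per dose and 93.9% for at least one. The plan states 85% and 93%.
- Dropout: 142/0.8 = 177.5, rounded up to 178, and 71/0.8 = 88.75, rounded up to 89. 178 + 89 + 89 = 356.

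The plan's figures reproduce, with no explicit allowance for baseline adjustment.

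**2. Cost of a common slope.** Let R be the residual covariance over the five visits, β the visit slopes and V the baseline variance. With complete data the common slope tends to Σ wβ, where w = R⁻¹1 / (1′R⁻¹1). With d the Day 28 slope minus the common slope, the variance of the Day 28 contrast is

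(1/n₁ + 1/n₀) × [R₂₈ + d²V].

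A baseline-by-day term removes d²V, so the relative inflation is d²V/R₂₈. Slopes for score and for change differ by exactly 1 at every visit, so d is the same on either scale.

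**3. Assumptions.** None of the following is in the documents except the SD of 12. Baseline SD is 4.5, 5.5 or 6.5. Visit SDs either rise (7.5, 9, 10, 10.8, 11.5) or are flat at 12. Correlation is AR(1) at 0.8 or 0.5. Slopes of change on baseline either move linearly from Day 2 to Day 28 (−0.20 to −0.45, or −0.15 to −0.60), or Day 2 alone differs (−0.20 against −0.45).

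Day 28 variance inflation in %, for the three baseline SDs in order:

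| Visit SDs | AR(1) | Day 2 weight | Linear, gap 0.25 | Linear, gap 0.45 | Day 2 alone off by 0.25 |
|---|---|---|---|---|---|
| Rising | 0.8 | 0.86 | 0.65, 0.97, 1.36 | 2.11, 3.15, 4.39 | 0.71, 1.06, 1.49 |
| Rising | 0.5 | 0.50 | 0.43, 0.64, 0.90 | 1.39, 2.08, 2.90 | 0.24, 0.36, 0.50 |
| Flat | 0.8 | 0.38 | 0.22, 0.33, 0.46 | 0.71, 1.06, 1.49 | 0.13, 0.19, 0.27 |
| Flat | 0.5 | 0.29 | 0.22, 0.33, 0.46 | 0.71, 1.06, 1.49 | 0.07, 0.11, 0.15 |

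Two entries by hand:

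- Flat SDs, linear gap 0.45: by symmetry d = 0.225, and 0.225² × 6.5²/12² = 1.49%.
- Flat SDs, AR(1) 0.8, Day 2 alone: the Day 2 weight is 1/(5 − 3 × 0.8) = 0.385, so d = 0.385 × 0.25 = 0.096, and 0.096² × 6.5²/12² = 0.27%.

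Of the 36 entries, 31 are below 1.5%. In participants, 356 × 1.5% is about 5 and 356 × 4.4% about 16. If Day 2 alone were off by 0.45, the worst row would reach (0.86 × 0.45)² × 6.5²/11.5² = 4.8%.

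**4. Day 2.** When Day 2 alone departs, its own gap is (1 − Day 2 weight) × 0.25. Flat SDs, AR(1) 0.8, baseline SD 6.5: (0.615 × 0.25)² × 6.5²/12² = 0.69%. Rising SDs, AR(1) 0.8: (0.14 × 0.25)² × 6.5²/7.5² = 0.09%. Where the common slope leans on Day 2, Day 28 bears the cost; otherwise the two share it.

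**5. Power.** Take 12 as the residual SD under the planned model, d = 0.3 and baseline SD 4 to 8. The variance falls by 0.09 × 16/144 = 1.0% to 0.09 × 64/144 = 4.0%. The SE goes from 1.744 to between 1.735 and 1.709, and power per dose from 85.8% to between 86.2% and 87.3%.

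**6. With dropout.** A simulation used 356 participants, about 17% MAR dropout, an unstructured MMRM without center and antidepressant status, 250 runs per scenario and baseline SD 4 to 8. Adding the interaction changed the model SE by about 0% (equal slopes), by −0.3 to −1.2% (score slope 0.9 at Day 2, 0.6 after) and by −0.7 to −2.3% (score slope falling from 0.95 to 0.55). Under both models the mean estimates stayed within simulation error of the true −5.4.

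**The case against.** The strongest case against is that this is a modelling preference. Nothing in the documents shows that slopes differ. The recall difference concerns Day 2, and Day 28 shares its 7-day recall with baseline and three other visits. A Day 2 mismatch reaches Day 28 only through the Day 2 weight, and the upper end of the range needs visit SDs that rise steeply and are highly correlated. With the one SD the plan states, held flat, no entry exceeds 1.5%. The model is also reused in several places, and the SAP is already at version 4.0.

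All of this stands and limits the size of the point. None of it shows a disadvantage of the extra term: d²V cannot be negative, and four parameters among 356 participants cost almost nothing.

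A reader might infer that the primary test is biased or its standard error wrong. That does not follow. With complete data, randomization keeps the contrast unbiased, and the unstructured covariance absorbs the misfit, so the reported SE is honest.

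A reader might also extend the recall argument to the PHQ-9 analysis in SAP 5.5.5.2. It does not carry over. The PHQ-9 has a single 2-week recall, and with two post-baseline visits the interaction would cost one parameter, not four.

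**Conclusion.** A low-cost improvement, not an error. The planned model restricts the baseline slope to be equal across visits while leaving the treatment effect and covariance free. The schedule gives a plausible reason, but no proof, that the slopes differ. Under the stated assumptions the Day 28 residual variance is about 0.1 to 4.4% larger than needed, mostly under 1.5%, and there is no loss if slopes are equal. It is tempting to say that the plan does give up precision at Day 28, or that the trial is short of participants. The documents support neither: they contain no baseline SD, visit slopes or visit correlations, and the stated 85% and 93% power reproduces without help from baseline adjustment.

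**What to change.** Before unblinding, add a baseline MADRS-by-day interaction to the MMRM in Protocol 9.4.2 and SAP 5.3.2.1.1. Carry it to the Day 2 analysis (5.4.1.3) and to the reused MMRM in Step 2 of the tipping-point analysis (5.3.2.1.2) and of the supplementary analysis (5.3.3.1). The analysis model will then match the imputation model in 5.3.2.1.2, which already lets the baseline coefficient differ by visit.

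SAP 5.5.5.2 takes its model from the primary analysis by reference, so state there whether the term applies to PHQ-9; the recall argument gives no reason for it. SAP 5.5.11 lists its own terms and needs an explicit decision.

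The cost is four parameters (five slopes instead of one), a short edit in two documents, and no new data.

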5.3.2.1.2. Sensitivity Analysis

To evaluate the robustness of the MMRM analysis to increasing deviations from the MAR assumption, a delta adjustment multiple imputation method will be implemented on the MADRS total score if the results from the primary analysis show a significantly greater improvement in

MADRS total score at Day 28 in each dose of esketamine nasal spray compared to placebo. (National Research Council 2010; Permutt 2015)

This method will employ the following 3 steps:

Step 1 – Multiple Imputation (MI)

Missing at random (MAR) is assumed for intermediate missing data (ie, missing data between non-missing observations). If there are participants with a non-monotone missing data pattern, datasets with only monotone missing data patterns will be created first by imputing the intermediate missing values using methods such as the MCMC (Markov Chain Monte Carlo) method. Five hundred (500) imputations will be performed to create 500 unique datasets which now have monotone missing (ie., missing data after the participant experienced an intercurrent event) data pattern. This will be done using SAS PROC MI and the MCMC statement with the following specifications (in case of non-convergence, analysis center will be removed from the following model):

```
PROC MI DATA=INPUT NIMPUTE=500 SEED=234 OUT=IN MCMC;
```

VAR ...; (intervention group, analysis center, antidepressant treatment status, and the preceding non-missing values in the order of clinical visits: baseline, Day 2, Day 8, Day 15, Day 22 and Day 28)

MCMC CHAIN=SINGLE NBITER=200 NITER=100 IMPUTE=MONOTONE; RUN;

Monotone missing data will first be imputed by MAR-based MI regression, and the imputed scores in the experimental intervention groups will be adjusted to be worse than the other participants in same group with non-missing data as discussed below. The multiple imputation will be performed using SAS PROC MI with the MONOTONE statement and the REGRESSION option with the following specifications (in case of non-convergence, analysis center will be removed from the following model):

```
PROC MI DATA=IN_MCMC NIMPUTE=1 (see note) SEED=234 OUT=OUTPUT; BY IMPUTATION;
```

VAR ...; (intervention group, analysis center, antidepressant treatment status, and the preceding non-missing values in the order of clinical visits: baseline, Day 2, Day 8, Day 15, Day 22 and Day 28)

CLASS ...; (intervention group, analysis center, antidepressant treatment status) MONOTONE REGRESSION;

RUN:

*Note: NIMPUTE=500 if MCMC was NOT applied at the previous step.

The imputed values for subjects who discontinued DB treatment [QX[1]]will be adjusted by adding δ_c to the imputed values for participants randomized to the control group and adding δ_A to the imputed values for participants randomized to the experimental intervention groups. Delta-adjusted fully imputed datasets will be generated for different combinations of δ_c and δ_A values as defined below:

- $\delta_c = 0$ and $\delta_A = 0$ to Δ^* in increments of 1 (experimental group-only adjustment analysis)
 - Adding positive values results in higher (worse) scores. Δ* represents the adjustments leading to the 'tipping point', so the smallest delta adjustments values at which conclusions change from favorable (ie, statistically significant: 2-sided p-values for both doses ≤0.05 in favor of esketamine, or the smaller 2-sided p-value ≤0.025 in favor of esketamine) to unfavorable (fail to reject the null hypothesis of no intervention difference).

These methods will be applied to all missing data under hypothetical strategy.

Step 2 – Analysis

Same MMRM analysis as described for the primary efficacy analysis (Section 5.3.2.1.1) will be performed for each set of the adjusted fully imputed datasets.

Step 3 – Pooling

Rubin's methodology will be applied to the MMRM results from the 500 imputed datasets to produce final inferences. (Rubin 1987)

Between-group comparisons to placebo at Day 28 (eg, 2-sided p-values, point estimates for intervention difference) will be displayed for each considered δ_A , up to the 'tipping point' adjustment.

